4.6 Blind Review

The results of the final data assessment will be documented in the final list of important deviations, validity findings and assignment to analysis set(s). Any changes to the statistical analysis prompted by the results of the review of study data will be documented in an amendment and, if applicable, in a supplement to this SAP.

5. Analysis Sets

5.1 Assignment of analysis sets

Final decisions regarding the assignment of subjects to analysis sets will be made during the review of study data and documented in the final list of important deviations, validity findings and assignment to analysis set(s) (see section 4.6).

The statistical analysis sets are defined as follows:

Safety analysis set (SAF)

All subjects with at least one intake of study drug.

Per protocol set (PPS)

All SAF subjects who completed Part A and Part B of the study with no major protocol deviations.

Pharmacokinetic Analysis Set (PK set)

All SAF subjects with evaluable PK profiles.

Subjects who were assigned to treatment but did not receive study medication will not be included in the SAF. As the number of these excluded subjects is anticipated to be negligible, if at all any exist in this design, an “all assigned treatment analysis set” will not be generated.

Subjects who do not belong to SAF will not be included into statistical considerations. These subjects are classified as ‘listing only set’ (LOS). Number of screening failures and dropouts will be tabulated.

6. Statistical Methodology

The efficacy analyses will be based on the PPS and sensitivity analyses will be based on the SAF as appropriate.

The primary analysis population for the safety analysis will be the SAF.

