Multiple-dose escalation component: Eight (8) new distinct subjects are planned to be enrolled in each of the 3 dose cohorts. Opening of the new cohort will only enroll new subjects. An initial dose of 100 mg SC has been selected for Dose X based on safety and PK/PD data from the Phase I study. Safety data from Dose X in N=6 subjects after 1x/week SC dose for 6 weeks will be the basis for opening the cohort for Dose Y. When acceptable safety and tolerability has been achieved in the first 6 subjects after 6 weeks of dosing, the cohort for Dose Y (not to exceed 250 mg) will be opened for enrollment of 8 new subjects. The opening of cohort to Dose Z (dose not to exceed 400 mg) follows the same process and will be based on safety/tolerability data from N=6 subjects given Dose Y once weekly for 6 weeks.

The DMC will review all available safety data and the proposed dose based on PK/PD prior to opening any cohort. Safety evaluation, including stopping criteria, is described in Sections [9.6.1.7](#) and [13.1.2](#).

Dose-finding component: This portion of the study is designed to allow for identification of the appropriate dose(s) for the Phase 3 study. The dose selection for Phase 3 will be based on both the assessment of safety and evidence of efficacy based on bleeding control assessed over a 12-week period of dosing. In each cohort at dose level X, Y and Z the subjects will continue at that dose for at least 12 weeks and efficacy information from all 8 subjects at each dose level will be used for the assessment of efficacy (based on number of bleedings). Although acceptable safety and tolerability data of 6 weeks in at least 6 subjects at Dose X is required to open the next cohort – Dose Y, all 8 subjects at Dose X will remain at dose level X for at least 12 weeks to assess the efficacy. If the next dose level is open, patients in dose level X or Y will be allowed to escalate to the next dose level after 12 weeks of treatment with BAY 1093884 if specific conditions are satisfied. First, safety criteria as defined in the protocol must be met. Second, the patient must have experienced >2 bleeds during the first 12 weeks of treatment or experienced >1 bleed during any 12-week interval after the first 12 weeks of treatment at a particular dose level. The safety criteria to be assessed for this portion of the study (individual dose escalation after 12 weeks of dosing in that particular dose cohort) are provided later in this section.

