Eight (8) new distinct subjects are planned to be enrolled in each of the 3 dose cohorts. Opening of the new cohort will only enroll new subjects. These subjects will be treated prophylactically with the X Y or Z dose of BAY 1093884 once weekly for 12 weeks (part A). At least 1 inhibitor subject (any titer) and 2 PK subjects (willing to undergo full PK evaluations) will be enrolled in each cohort.

All subjects of each cohort will continue on the dose assigned for Part A (12 weeks) to obtain safety data and individual efficacy data.

Individual subject dose escalation criteria in the dose finding part of the study:

In this portion of the study, the objective is to identify the appropriate dose(s) for the Phase 3 study. The dose selection for Phase 3 will be based on both the assessment of safety and evidence of efficacy based on individual bleeding control assessed over a 12-week period of dosing for each patient.

Subjects will be evaluated for the number of bleeds occurring during each part of the study. In particular, only the bleeds recorded as “spontaneous” (not related to any trauma or activity) and requiring additional treatment will be considered for the dose escalation efficacy evaluation, and are defined below as “bleeds.”

Evaluation at the end of Part A:

Subjects who present ≤ 2 bleeds during Part A will start Part B and continue on the same weekly dose; otherwise (if presenting >2 bleeds) subjects will escalate to the next higher opened dose cohort.

Evaluation at the end of every 12-week period of Part B and extension:

Subjects who present ≤ 1 bleed in 12 weeks, during Part B, or during the extension part, will continue on the same weekly dose; otherwise (if presenting >1 bleed) subjects will escalate to the next higher opened dose cohort.

Since dose Z is the highest dose, any subject on dose Z who meets the escalation criteria described above may withdraw from the study or may continue treatment to provide further safety and efficacy data. The decision on treatment continuation is at the subject’s and investigator’s discretion.

The first injection of any new or escalated dose will be given under medical supervision

If a subject qualifies for dose escalation based on the number of bleeds, but the next higher dose cohort has not been opened, the subject must stay on the current dose and then escalate to the next higher dose only after it is opened.

Dose selection for cohorts:

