6.3 Withdrawal of subjects from study

6.3.1 Withdrawal

Withdrawal criteria

Subjects *must* be withdrawn from the study if any of the following occurs:

- At their own request or at the request of their legally acceptable representative. At any time during the study and even without giving reasons, a subject may decline to participate further. The subject will not suffer any disadvantage as a result.
- Development of an inhibitory antibody to BAY 1093884 that neutralizes the activity sufficiently to interfere with effective treatment.
- Failure to comply with scheduled appointments for study-related testing or with Electronic Patient Diary (EPD) data entry to an extent that compromises collection of critical data
- Significant concurrent illness or deterioration in the subject's condition, including laboratory values that the investigator deems to be incompatible with the subject's continued safe participation in the study.

In all cases, the reason for withdrawal must be recorded in the case report form (CRF) and in the subject's medical records

At the time of discontinuation, the subject should be scheduled to perform the procedures and evaluations required at the final study visit.

Subjects *may* be withdrawn from the study if any of the following occurs:

- Violation of eligibility criteria;
- Withdrawal of a subject at the specific request of the Sponsor;
- Withdrawal of a subject at the Investigator's request. As examples: If the Investigator considers that the subject's health is compromised by remaining in the study or if a subject on the highest dose (without possibility for dose escalation) presents excessive uncontrolled bleeding; or the subject is not sufficiently cooperative;
- Withdrawal of a subject from the study if the subject is lost to follow-up.

Depending on the time point of withdrawal, a withdrawn subject is referred to as either "screening failure" or "dropout" as specified below:

Screening failure

A subject who, for any reason (e.g., failure to satisfy the selection criteria), terminates the study before the time point used for the definition of "dropout" (see below) is regarded a "screening failure."

Re-starting the defined set of screening procedures to enable the "screening failure" subject's participation at a later time point is not allowed – with the following exceptions:

- The subject had successfully passed the screening procedures, but could not start subsequent treatment on schedule.

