- Initial screening occurred too early to complete the required washout period after prior therapy.
- The in-/exclusion criteria preventing the subject's initial attempt to participate have been changed (via protocol amendment).

Thus, participation of an initial "screening failure" subject at a later time point even if he meets all selection criteria upon re-screening is not acceptable.

In any case, the investigator has to ensure that the repeated screening procedures do not expose the subject to an unjustifiable health risk. In addition, the subject must re-sign the informed consent form during re-screening, even if it was not changed after the subject's previous screening. If a subject is re-screened, he will be assigned a new subject number.

Dropout

A subject who discontinues study participation prematurely for any reason is defined as a "dropout", if the subject has received at least 1 dose of BAY 1093884.

General procedures

In all cases, the reason for withdrawal must be recorded in the electronic case report form (eCRF) and in the subject's medical records.

The subject may object to the generation and processing of post-withdrawal data as specified in Section 13.4.

Completer

A subject is defined as completer if he has completed at least Part A, a minimum of one Part B, and has performed a final visit.

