7.1.4 Treatment for minor and major surgery

In the event a subject requires an unplanned minor surgery during the interventional part of the study, the treatment schedule with BAY 1093884 will not be affected. As for the treatment of bleeds (see Section 7.1.2), the subject's pre-study hemophilia treatment can be administered, as required. It may be tailored to the subject's individual response.

The appropriate treatment of minor surgery is left to the discretion of the treating physician and/or local clinical practice.

Minor surgery is defined as any surgical procedure that does not meet the definition of major (see below), and may include (but is not restricted to) dental extractions, incision and drainage of an abscess, or excisions.

Major surgery is defined as any surgical or invasive procedure (elective or emergent) in which the overall bleeding risk may be excessive, would require a general anesthetic in an individual without a bleeding disorder, penetrates or exposes a major body cavity, could result in substantial impairment of physical or physiological functions, or requires special anatomic knowledge or manipulative skill (e.g., tonsillectomy, laparotomy, thoracotomy, joint replacement).

If major surgery is required during the subject's first 24 weeks of treatment (i.e., during Part A and B), the subject will be withdrawn from the study. If major surgery is required

after the first 24 weeks, the subject may use his own hemophilia medication and prophylaxis treatment with BAY 1093884 will be interrupted. In this case, following surgery, the subject may re-enter the study and restart prophylaxis with BAY 1093884 after discussion with the sponsor.

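### The per-protocol set requires completion of Part A and Part B, so a subject who leaves before week 24 is dropped from the 12-week Part A responder rate even when his Part A bleed count is complete

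*SAP*

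**What the plan says.** SAP section 5.1 and Protocol section 10.2 define a single PPS: "All SAF subjects who completed Part A and Part B of the study with no major protocol deviations". SAP section 6 and Protocol section 10.2 then make it the main efficacy set: "The efficacy analyses will be based on the PPS and sensitivity analyses will be based on the SAF as appropriate". SAP section 6.2 lists three responder variables with exact 90% Clopper-Pearson intervals. One is the number of subjects with at most 2 treated spontaneous bleeds in Part A, the first 12 weeks. No separate analysis set for Part A is visible.

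The design text reads differently. In the dose-finding component of Protocol section 5, repeated in SAP section 3, "efficacy information from all 8 subjects at each dose level will be used for the assessment of efficacy".

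The end of Part B is placed at about week 24. Primary completion is 24 weeks of treatment for the last Cohort 3 subject. Protocol section 6.3.1 calls a subject a completer if he "completed at least Part A, a minimum of one Part B, and has performed a final visit". Protocol section 7.1.4 equates the first 24 weeks with Parts A and B.

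**The concern.** Whether a subject responded in Part A is known at week 12. Under the PPS, whether he is counted depends on what happens between weeks 12 and 24. The SAP warns about restriction on post-baseline events for the Part B analyses, but does not note that the PPS imposes the same kind of restriction on Part A.

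The selection can be related to outcome and can differ by dose. Under Protocol section 5, "any subject on dose Z who meets the escalation criteria described above may withdraw from the study or may continue treatment". Protocol section 6.3.1 gives as an example of investigator withdrawal "if a subject on the highest dose (without possibility for dose escalation) presents excessive uncontrolled bleeding". Dose X and Y subjects with the same bleeding escalate or stay on their dose, and can remain in the PPS. These written bleeding exits therefore fall on dose Z.

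Other exits apply at every dose and may remove responders as well as failures:
- the subject's own request;
- stopping because of response or satisfaction;
- "Development of an inhibitory antibody to BAY 1093884 that neutralizes the activity sufficiently to interfere with effective treatment";
- major surgery in the "first 24 weeks of treatment (i.e., during Part A and B), the subject will be withdrawn from the study".

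Protocol section 5 says the Phase 3 dose choice will rest on safety and on bleeding control over 12 weeks. The PPS rate would describe only those who stayed to week 24.

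**Working it through.** **The plan's own figure.** 3 cohorts x 8 = 24, as stated. There is no power calculation to reproduce.

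**Can the PPS keep all 8?** Only if nobody leaves before completing Part B and nobody has a major deviation. The replacement rule in Protocol section 6.3.2 targets 6 subjects at 6 weeks, plus minimum numbers of PK and inhibitor subjects. It does not aim for 8 completers. With an assumed loss d before the end of Part B, the chance that a cohort of 8 loses at least one subject is 1 - (1 - d)^8: 34% at d = 5%, 57% at 10% and 90% at 25%.

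**Effect on one cohort** (exact 90% Clopper-Pearson):

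| Leaves in Part B | All 8 | PPS |
|---|---|---|
| 2 failures | 6/8 = 75% (40-95) | 6/6 = 100% (61-100) |
| 1 failure | 7/8 = 88% (53-99) | 7/7 = 100% (65-100) |
| 1 responder | 5/8 = 63% (29-89) | 4/7 = 57% (23-87) |

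**Average shift under an assumed model.** Bleeds are gamma-Poisson with shape 1. The Part A mean is mu = rate x 84/365.25. The true response rate is p = P(at most 2 bleeds) = 1 - (mu/(1+mu))^3. If fractions qf of failures and qr of responders leave, the PPS rate is p(1-qr) / [p(1-qr) + (1-p)(1-qf)]. The rates of 1, 3 and 5 per year borrow the general prophylaxis figures in Protocol section 5 (1 to 3 without inhibitors, about 5 with). They are not rates of treated spontaneous bleeds.

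Example at 5 per year: mu = 5 x 84/365.25 = 1.150; p = 1 - (1.150/2.150)^3 = 0.847. With qf = 0.5 and qr = 0, the PPS rate is 0.847/(0.847 + 0.153 x 0.5) = 0.917, a shift of +7.0 points.

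| | 1/year | 3/year | 5/year |
|---|---|---|---|
| True Part A response | 99.3% | 93.2% | 84.7% |
| qf 0.5, qr 0 | +0.3 | +3.3 | +7.0 |
| qf 0.5, qr 0.25 | +0.2 | +2.2 | +4.6 |
| qf 0.25, qr 0.25 | 0 | 0 | 0 |
| qf 0, qr 0.25 | -0.2 | -2.1 | -4.1 |

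For qf = 0.5 and qr = 0, changing the shape (0.5, 1, 2, or plain Poisson) gives shifts of 0.1 to 0.6 points at 1 per year, 1.6 to 3.9 at 3, and 5.2 to 7.2 at 5.

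**How often it would occur.** With half of failures leaving, the number of failed leavers among 8 is binomial with probability 0.5(1-p). The chance of at least one is 3%, 24% and 47% at the three rates. The chance of two or more is 0.03%, 3% and 12%.

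**Comparing Y with Z.** Assume the doses are equally effective, with 8 subjects each, and enumerate exactly. Each cell gives how often Z has the higher observed rate / how often Y does; the remainder are ties.

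| Failures leaving | 3/year | 5/year |
|---|---|---|
| Nobody at either dose | 27.9% / 27.9% | 35.8% / 35.8% |
| Z 50%, Y 0% | 34.8% / 16.3% | 52.4% / 24.7% |
| Z 50%, Y 25% | 27.8% / 17.9% | 44.1% / 28.4% |
| Z 50%, Y 50% | 19.8% / 19.8% | 33.1% / 33.1% |

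The tilt towards Z comes from unequal loss and disappears when the loss is equal. At 1 per year it is slight (about 5% against 3% in the most unequal case).

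**The case against.** **Context of the design sentence.** It contrasts all 8 subjects with the 6 needed to open the next cohort, and it does not define an analysis set. That is fair, but it still says whose efficacy data will be used, and the PPS rule cannot deliver that once someone leaves early.

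**Part A response is not shown to be the lead efficacy variable.** It is one of three responder variables, and Protocol section 10.5 names subjects without treated spontaneous bleeds. This stands. The claim here is only that the PPS version is the main version of the Part A rate.

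**Completion of Part B is not sharply defined.** Part B consists of repeated 12-week periods. On any reading, though, a subject who leaves before week 24 has not completed it.

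**Redaction.** Parts of SAP section 6.2 and Protocol section 9.4 are blacked out, and an exception for Part A could be there. It cannot be ruled out; the visible general rule contains none.

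**Other analyses reduce the harm.** Protocol section 10.3.3 plans analyses of all available bleeding data. SAP section 6.2.1 includes annualized rates because they allow for drop-outs. The 2020 additional SAP gives annualized rates by initial dose with no stated completion requirement. Individual data are listed, so a reader could rebuild the rate for all treated subjects. This limits the damage, but none of it commits to a Part A responder rate in all treated subjects. The rule in SAP section 4.5.2 for subjects who discontinue in Part A has no role in the main set, because such a subject can never enter it.

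**The size rests on assumptions.** This also stands. Average shifts of 0.3 to 7 points are small beside a 90% interval of 40 to 95% at 6/8, and the two-failure example is uncommon in the model.

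**Conclusion.** The concern holds on the visible text and should be fixed. The main Part A rate depends on staying to the end of Part B, contrary to the stated use of all 8 subjects per dose level. Its bias has no known direction: upward if failures leave more often than responders, downward if responders leave more often, and none if both leave equally. The written bleeding exits specific to dose Z make unequal loss between doses plausible, not certain. The quantified shifts depend on assumed bleed rates, shape and leaving fractions. The primary safety analysis uses the SAF and is unaffected, and no error rate or power is involved. What is at risk is the description of bleeding control by dose that supports the Phase 3 choice.

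**What to change.** In SAP section 6 and Protocol section 10.2:

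1. Make the SAF by dose initially received the main set for bleed endpoints, with the PPS supportive.
2. Class every subject who completed Part A by his observed Part A bleeds, whatever happens later. This is the minimum change and by itself removes the dependence on a later event for Part A completers.
3. Count a subject who leaves during a 12-week period as a non-responder if he had already exceeded that period's bleed limit or left because of bleeding.
4. Show all other early leavers by reason, including antibody withdrawals, counted once as responders and once as non-responders.
5. Compute annualized bleed rates in the SAF over observed time with the existing SAP section 4.5.2 rules.
6. Keep the SAP section 6.2 caution about escalated subjects in Part B.

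The cost is wording and a little more analysis. No new data are needed. Response rates may look less favourable.

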6.1 Population characteristics

6.1.1 Demography and baseline characteristics

Demographic and baseline data will be evaluated descriptively for the SAF as well as for the PPS and PK set, by treatment groups and overall. No statistical tests will be performed to compare these characteristics across treatment groups.

Descriptive statistics (such as mean, standard deviation, median, quartiles, minimum and maximum) will be provided for continuous variables such as

- age at Screening,
- body weight,
- body height.

Counts and (appropriate) percentages will be provided for categorical variables such as

- year of birth,
- sex,
- race/ethnicity.

Reasons for exclusion from analysis populations will be summarized.

6.1.2 Medical history

Medical history data will be evaluated by frequency tables, showing the number and percentage of subjects with medical history findings (i.e., previous diagnoses, diseases or surgeries) that started before signing of the informed consent and that are considered relevant for the subject's study eligibility using MedDRA Primary System Organ Class / Preferred Term.

6.1.3 Disease history

The following baseline characteristics of the disease history will be evaluated descriptively for the SAF as well as for the PPS, by treatment groups and overall in addition:

- Date of hemophilia diagnosis
- Start of therapy
- Current FVIII or FIX products (product, dose and frequency of administration)
- Current by-passing agents (product, dose and frequency of administration)
- Number of exposure days
- Type of FVIII or FIX gene mutation (from history)
- Family history of hemophilia
- FVIII or FIX level and type of assay
- Family and personal history of past inhibitor formation
- Current inhibitor level
- Current ITI status
- Number and type of bleeds in the past 6 months

- Presence and location of target joints

6.1.4 Medication history

Medication history data including include prior and current FVIII/FIX products and bypassing agents used for hemophilia treatment as well as a history of other prior and current medications will be evaluated descriptively for the SAF as well as for the PPS, both overall and by treatment groups. This includes:

- Medication trade name and dose (including food supplements)
- Reason for medication
- Start date and end date

6.2 Efficacy

CCI
[Redacted text block containing multiple paragraphs of blacked-out content]

All endpoints will be summarized by descriptive statistics.

The responder variables (number of subjects in each 12-week Part B period with ≤ 1 spontaneous bleed requiring treatment, number of subjects without spontaneous bleeds requiring treatment in addition to BAY 1093884, number of subjects in Part A with ≤ 2 spontaneous bleeds requiring treatment in addition to BAY 1093884) will be estimated together with 90% confidence intervals based on exact method (Clopper-Pearson).

For the analysis on each 12-week Part B period, only subjects who were not escalated are taken into account. It should be noted that this kind of analysis must be interpreted carefully, as the restriction is based on post-baseline events.

The variables number of subjects without spontaneous bleeds requiring treatment in addition to BAY 1093884, total number of spontaneous bleeds requiring treatment in addition to BAY 1093884 and number of muscle, joint, target joint, spontaneous, non-spontaneous/non-traumatic, traumatic and all bleeds (requiring treatment in addition to BAY 1093884) will be descriptively analysed on Part A, on each 12-week Part B period and on combination of these. For the analyses which are based on Part B, only subjects who were not escalated are taken

into account. It should be noted that this kind of analysis must be interpreted carefully, as the restriction is based on post-baseline events.

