10.5 Planned interim analyses

After all subjects still participating in the study have completed Part A and at least one 12-week Part B period (primary completion) of the study, all dose levels will be assessed including clinical safety, routine safety laboratory, hemostasis and thrombosis markers as per PK/PD assessment and clinical efficacy.

For safety, AEs will be assessed for all subjects per dose level. In case of comparable clinical safety, the routine lab findings will be evaluated. In case of comparable clinical and laboratory safety, thrombosis and hemostasis markers will determine safety evaluation.

For efficacy, the number of subjects without spontaneous bleeds requiring treatment in addition to BAY 1093884 will be assessed; all other efficacy variables will be assessed for the dose levels observed.

11. Data handling and quality assurance

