4.2 Handling of Dropouts

In this study, all efforts must be taken to engage patients to comply with all study procedures and to continue to be followed until the end of the study.

A subject who discontinues study participation prematurely for any reason is defined as a “dropout” if the subject has received at least 1 dose of BAY 1093884. A subject is regarded a “screening failure” if he terminates the study for any reason (e.g., failure to satisfy the selection criteria) prior to the time point used for the definition of “dropout” .

In all cases, the reason for withdrawal must be recorded in the electronic case report form (eCRF) and in the subject's medical records.

The number of subjects who prematurely discontinue the study during the treatment phase or during the post-treatment observation phase for any reason, as well as the reasons for premature discontinuation of study, will be displayed by dose cohort and dose actually received. Baseline characteristics will be displayed by premature discontinuation (yes/no) from study.

Subjects who drop from the study after first administration of study treatment will be included in a listing in addition to the inclusion into the SAF.

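### In the SAF responder tables, a subject who leaves within a 12-week period while still below the bleed threshold counts as a responder or as bleed-free, and the PPS removes him, so neither set shows him as a failure

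*SAP*

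**What the plan says.** SAP 6.2 names three responder variables: "number of subjects in Part A with ≤ 2 spontaneous bleeds requiring treatment in addition to BAY 1093884", "number of subjects in each 12-week Part B period with ≤ 1 spontaneous bleed requiring treatment" and "number of subjects without spontaneous bleeds requiring treatment in addition to BAY 1093884". Each is reported as a proportion with an exact 90% confidence interval. The readable text attaches no requirement that the subject was treated or observed to the end of the period.

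On analysis sets, the opening of SAP Section 6 states: "The efficacy analyses will be based on the PPS and sensitivity analyses will be based on the SAF as appropriate". Under SAP 5.1 the SAF needs one dose only, while the PPS needs both parts finished without a major deviation. SAP 4.2 says that a subject who drops out after the first dose "will be included in a listing in addition to the inclusion into the SAF". It also displays the number of premature discontinuations and their reasons by dose, but gives these subjects no responder status. SAP 4.3 deals with missing bleed details, bleed dates and AE dates, not with weeks that were never observed. Protocol 10.3.3 had deferred a detailed missing-data plan to the SAP.

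For the annualized bleed rate the position is different. SAP 4.5.2 sets an end time for subjects who discontinue, and SAP 6.2.1 says that this endpoint allows for unequal follow-up, dropouts included.

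Protocol 10.5 uses one of the same counts when the dose levels are assessed at primary completion: "the number of subjects without spontaneous bleeds requiring treatment in addition to BAY 1093884 will be assessed".

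**The concern.** A threshold on a count is easier to meet the shorter a subject is watched. A subject who takes one injection and leaves has no treated spontaneous bleeds. One who leaves at Week 3 with two such bleeds meets the Part A criterion. In the SAF both are successes, and in the PPS both disappear.

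Some exits are related to treatment and can happen below the threshold. Protocol 6.3.1 requires withdrawal for a neutralizing antibody, and Protocol 9.6.3.1 calls for removal after a confirmed hypersensitivity event. A dose with more such exits could show a higher SAF responder proportion for that reason. The study is meant to inform the Phase 3 dose from bleeding control over 12 weeks (Protocol Section 5). The SAF tables are where a reader would look to see whether excluding non-completers from the PPS made a dose look better than it is.

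**Working it through.** The documents state no responder rate, dropout rate or interval, so there is no figure of theirs to reproduce.

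**Inputs from the documents.** 8 subjects per cohort (SAP Section 3); thresholds of 2, 1 and 0 (SAP 6.2); exact 90% intervals (SAP 6.2); at least 8 bleeds per year before entry, of any type, treated or not (Protocol Section 5, with 6.1).

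**Assumptions.** Bleeds follow a Poisson process with the same rate in leavers and completers. The true rate of treated spontaneous bleeds on treatment is 8 to 16 per year, with 4 as a low-side check. Two of 8 leave at Week 4, with 1 to 3 as the range.

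**Step 1: chance of meeting the criterion by time observed.** Mean = rate × days / 365.25. P(≤2) = e^(−m)(1 + m + m²/2); P(0) = e^(−m).

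| Rate per year | Mean, 12 wk | Mean, 4 wk | P(≤2), 12 wk | P(≤2), 4 wk | P(0), 12 wk | P(0), 4 wk |
|---|---|---|---|---|---|---|
| 4 | 0.920 | 0.307 | 93.4% | 99.6% | 39.9% | 73.6% |
| 8 | 1.840 | 0.613 | 72.0% | 97.6% | 15.9% | 54.2% |
| 16 | 3.680 | 1.227 | 28.9% | 87.4% | 2.5% | 29.3% |

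**Step 2: expected SAF proportion for ≤2 in Part A, 2 of 8 leaving at Week 4.**
- Rate 8: observed count (6 × 72.0 + 2 × 97.6)/8 = 78.4%, against 72.0% with full follow-up (+6.4 points). Leavers as non-responders: 6 × 72.0/8 = 54.0%.
- Rate 16: (6 × 28.9 + 2 × 87.4)/8 = 43.5%, against 28.9% (+14.6 points). Leavers as non-responders: 6 × 28.9/8 = 21.7%.
- Rate 4: 2 × (99.6 − 93.4)/8, less than 2 points.
- With 1 to 3 leavers the observed count is 75.2% to 81.6% at rate 8 and 36.2% to 50.8% at rate 16.

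**Step 3: the same for bleed-free in Part A.** The shift is 2 × (P at 4 wk − P at 12 wk)/8. Rate 4: 2 × (73.6 − 39.9)/8 = 8.4 points. Rate 8: 2 × (54.2 − 15.9)/8 = 9.6 points. Rate 16: 2 × (29.3 − 2.5)/8 = 6.7 points.

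**Step 4: one cohort, three scorings.** Suppose 2 of 8 leave below the threshold and all 6 completers respond.
- SAF, observed count: 8/8 = 100% (90% CI 68.8% to 100%).
- SAF, leavers as non-responders: 6/8 = 75% (40.0% to 95.4%).
- PPS: 6/6 = 100% (60.7% to 100%).

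Each leaver is worth up to 1/8 = 12.5 points.

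**Step 5: what the annualized rate adds.** Two bleeds with exit at Week 4 give 2 × 365.25/28 = 26.1 per year. Two bleeds over 84 days give 2 × 365.25/84 = 8.7. The subject who left looks worse, as he should. With zero bleeds the rate is 0 at any follow-up time, so the early exit does not show.

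**The case against.** The case against has real weight. The list of responder variables follows a redacted block, and the opening of Protocol 9.4, where the efficacy variables are listed, is redacted too. A completion condition could stand in either place. The conclusion is therefore limited to the readable text, although the readable dropout and missing-data sections contain no such rule. The SAF analysis is also only "as appropriate", efficacy is descriptive, and safety is the primary endpoint.

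A reader might infer more than the documents support:
- *That every withdrawal is scored as success.* A subject above the threshold when he leaves stays a non-responder. Those who leave for heavy bleeding mostly fail already, and any treated spontaneous bleed ends bleed-free status. For Part B, only an exit within a period matters.
- *That the Protocol 10.5 dose assessment scores leavers as successes.* Section 10.5 names no set, but Protocol 10.2 bases efficacy on the PPS, which has no early leavers.
- *That the SAF counts are the only view of dropout, and always favour the drug.* The annualized rate moves against the drug when a leaver has bled, and SAP 4.2 already displays discontinuations by dose.
- *That two leavers raise the proportion by 25 points*, say from 4/8 (19.3% to 80.7%) to 6/8 (40.0% to 95.4%). This assumes that both would certainly have failed. The expected shift in Step 2 is about 6 to 15 points.

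Scoring every leaver as a failure is also biased: at a rate of 8 it gives 54.0% against 72.0%, an 18-point shortfall, larger than the 6.4-point excess that it replaces.

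**Conclusion.** The point holds on the readable text, within narrow limits. Applied as written, the SAF responder tables count a below-threshold early leaver as a responder or as bleed-free, and the PPS drops him. The annualized rate does not reveal a zero-bleed exit.

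The size depends on the assumed rates, the Poisson model and the number and timing of exits, none of which the documents give. With 2 of 8 leaving at Week 4, the expected excess in the Part A ≤2 proportion is about 6 points at 8 bleeds per year and 15 at 16. It is less than 2 points at 4 per year, where the bleed-free measure still shifts by about 8. What is affected is a descriptive proportion and its lower confidence limit. No test is planned, so type I error is not in question.

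**What to change.** In SAP 6.2, show the SAF responder tables in two versions side by side: (a) the observed count; (b) subjects who stop BAY 1093884 or leave before the end of the 12-week period counted as non-responders and not bleed-free. Give the number of such subjects and their reasons per dose. A leaver below the threshold is a success in (a) and a failure in (b), and one above it fails in both. The count that full follow-up on the dose would have given therefore lies between the two. The SAP should also say whether a temporary suspension counts as stopping. If the Protocol 10.5 assessment is run on any set other than the PPS, show both versions there too.

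The cost is SAP wording and an extra row per table. The treatment and visit dates are already needed for the annualized rate. If tables already exist, version (b) can be added as a labelled supplementary row. The downside is that (b) is conservative: exits for unrelated reasons, such as major surgery or closure of the study, count as failures. It should not be shown alone. If the redacted text already holds a rule for incomplete periods, a cross-reference in the tables is enough, with (a) and (b) kept as bounds.
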